This study uses a multi-site, randomized control trial. The effects of this intervention will be tested using a two-arm randomized controlled trial, comparing the mindful parenting program (Arm 1), to waitlist control group (Arm 2). Assessments will be made before (T0), 1-month follow up (T1), and 3-month follow-up (T2). The programme effects will be tested using both between-subject (comparison of the two arms) and within-subject (comparison of measures at T1, T2, and T3).

Sample size estimation. An estimated 340 parents will be recruited and randomised into an intervention group and a waitlist control group. The sample estimation is based on an expected effect size of .33 for family functioning in the PI's pilot study, with an estimated drop-out rate of 15%, a two-tailed α error of 5%, 80% power, and a test of two independent groups.

Recruitment of participants. Inclusion criteria are: (1) parents of an adolescent with the age between 10 to 21; (2) parents with a score of Patient Health Questionnaire (PHQ-9) score of 2 or above. Exclusion criteria are: 1) parents with current self-reported psychiatric diagnoses of psychosis, alcohol or substance abuse, 2) parents experiencing personal or family crisis in last six months; (3) parents cannot speak Chinese.

The research project will be announced and promoted in five non-governmental organizations, and social media. All interested parents will be given an information sheet and a four minute video explaining the nature of the study. After providing consent to participate the study, a research assistant who is blinded to the personal data of the participants, will administer the random assignment using computer generated programming. Participants will be randomly assigned to mindful parenting program (Arm 1), or waitlist control group (Arm 2).

Procedures

Program plan. The themes and content are based on a brief mindful parenting program developed by the same principal investigator (Lo et al., 2016, Lo et al., 2019). Psychoeducation of stress and coping in the context of parenting relationship is infused. Instructors for the program possess a PhD in psychology or social work, a specialist in psychiatry, and foundational professional training in mindfulness-based cognitive therapy.

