Implementation and assessment. After the first assessment (T0), caregivers who meet inclusion criteria will be randomized into Arm 1 or Arm 2. After the intervention, two time points will be used to assess the intervention outcome and sustainable effect at one month and three month. Programs are delivered in group format and will be conducted in five sites, including the P-I's university and the service units of NGO collaborators. To ensure intervention fidelity, all program sessions will be audio-recorded and an independent rater will listen to 20% of the selected clips on random basis, and assess whether each element in the intervention protocol has been implemented with consistency. Higher concordance rates will signify greater fidelity to the intervention protocol, which will be carefully monitored throughout the study.

An Ethical approval for this study has been obtained from the Research Office of the Hong Kong Polytechnic University.

Measures

All measures of the variables are summarized in Table 1 below. In line with the study objectives and hypotheses, primary outcome variables include parental depression. Secondary outcome measures include anxiety, post-traumatic stress, perceived family functioning, family conflicts, and interpersonal mindfulness.

Data Analyses

Quantitative data analyses: Intervention effects. All analyses will be carried out according to the intention-to-treat approach. (Moher et al., 2010). MANOVA will be used to evaluate the effects of the mindful

parenting (Arm 1), relative to waitlist control group (Arm 2), and the analyses of the primary and secondary outcome measures. In addition to the immediate programme effects, outcomes measured at T1 and T2 will be compared, to assess whether maintenance effects will be sustained at 3-months.

Table 1. Outcome variables and measures

Study variables and measures
Depression - Measured by the Patient Health Questionnaire (PHQ-9, Kroenke et al., 2001), 9 items
Anxiety - Measured by the Generalized Anxiety Disorder 7-item (GAD-7, Kroenke, et al., 2016), 7 items
Post-traumatic stress - measured by the International Traumatic Questionnaire (ITQ, Cloitre et al., 2009), 6 items
Family functioning - Measured by 5 item, Family APGAR Scale (Smilkstein, Ashworth, & Montano, 1982), with five subscales in adaptation, partnership, growth, affection, and resolve.
Family conflict - measured by Conflict Tactics Scale (CTS-2, Straus & Gelles, 1979), 16 items

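### Five delivery sites, but the plan specifies neither stratification of the randomisation by site nor a site term in the MANOVA: a small, avoidable loss of precision

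*Combined protocol and SAP*

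**What the plan says.** Under Study design, the protocol states: "This study uses a multi-site, randomized control trial". Under Implementation and assessment: "Programs are delivered in group format and will be conducted in five sites". These sites are the principal investigator's university and service units of the collaborating organisations.

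Under Recruitment of participants, parents come from five non-governmental organisations and from social media. After consent, a research assistant blinded to personal data "will administer the random assignment using computer generated programming". Nothing more is said about the algorithm: not the ratio, blocking, strata or site.

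Under Data Analyses, the approach is intention-to-treat and "MANOVA will be used to evaluate the effects of the mindful" parenting arm relative to waitlist, for primary and secondary outcomes. No site factor, covariate or random effect is named.

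Under Sample size estimation: "An estimated 340 parents will be recruited and randomised into an intervention group and a waitlist control group". The calculation is a plain comparison of two independent groups, with 15% drop-out, two-sided 5% alpha and 80% power. "The sample estimation is based on an expected effect size of .33 for family functioning in the PI's pilot study".

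**The concern.** Site is a real feature of this design. Different organisations host the programme and may serve different families, so outcomes may differ between sites. A multi-site trial can deal with this in the allocation, by stratifying, and in the analysis, by fitting site. Neither is written down here, so one cannot be relied on to make up for the other.

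What is at stake is precision. With simple allocation, the arms can be uneven within a site, and an unadjusted comparison carries between-site variation as noise. These are two views of one cost, because chance site imbalance is already reflected in the unadjusted standard error. Planned power sits almost exactly at 80%, so there is no spare margin. There is also a practical side: Arm 1 runs in groups at sites, so an uneven split affects how groups are filled. And if a noticeable imbalance appeared, adding site afterwards would be a post hoc choice.

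**Working it through.** **Inputs from the plan.** 340 randomised, effect size .33, 15% drop-out, two-sided alpha 5%, power 80%, five sites.

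**Assumptions, not in the plan.** 1:1 allocation; equal sites; .33 is a mean difference divided by the total SD; a share *s* of outcome variance lies between sites, taken as 1% to 10%.

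**1. The plan's own figure.**
- Per arm: 2 × (1.960 + 0.842)² / 0.33² = 144.1, so 145; total 290.
- With drop-out: 290 / 0.85 = 341.2, so 342.
- The t-test version needs 146 per arm: 292 / 0.85 = 343.5, so 344. Multiplying by 1.15 instead gives 334 or 336.

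The stated 340 reproduces and contains no site element.

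**2. Balance within sites, if allocation is simple.** 340 / 5 = 68 parents per site, and the number in Arm 1 is Binomial(68, 0.5).
- Split of 28:40 or worse, either direction: 0.182 for a given site; for at least one of five, 1 − (1 − 0.182)⁵ = 0.63.
- Split of 26:42 or worse: 0.068 for a given site; for at least one of five, 1 − (1 − 0.068)⁵ = 0.30.

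**3. Power.** Completers per arm: 340 × 0.85 / 2 = 144.5. The noncentrality is d × √(144.5 / 2) = 8.5d.
- No site term: 8.5 × 0.33 = 2.805, which gives 79.8% (t-test; the normal approximation gives 80.1%).
- Stratified by site, with a site term: d becomes 0.33 / √(1 − s).
- Site term only, simple allocation with equal arm totals: chance imbalance across sites reduces the information on average by the factor 1 − 4/288 = 0.986, so the noncentrality is multiplied by √0.986 = 0.993.

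| Site share *s* (assumed) | d / √(1 − s) | Stratified + site term | Site term only |
|---|---|---|---|
| 1% | 0.332 | 80.2% | 79.7% |
| 2% | 0.333 | 80.6% | 80.1% |
| 5% | 0.339 | 81.8% | 81.3% |
| 10% | 0.348 | 83.8% | 83.3% |

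The 4 degrees of freedom themselves cost almost nothing (287 falls to 283). At a 1% share, the model term alone gives essentially no gain over 79.8%.

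**4. If allocation is in fact stratified but site is left out of the model.** The standard error used is too large by 1/√(1 − s), so the actual two-sided alpha is 2 × [1 − Φ(1.960 / √(1 − s))]: 0.049, 0.044 and 0.039 at shares of 1%, 5% and 10%. The test is slightly conservative.

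**The case against.** The strongest reply is that the gain is small and rests on an assumed variance share with no source in the documents. That stands. Stratification adds only about half a percentage point beyond the model term, and at a 1% to 2% share the model term alone adds almost nothing. The 63% figure also needs care: 28:40 is 41% against 59%, counted in either direction at any one of five sites, which is not an extreme split.

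A second reply is that the plan is silent, not wrong. That also stands. A reader might infer that the randomisation ignores site. The documents do not show this: they describe the allocation in a single phrase and give no algorithm, so the imbalance figures are conditional on simple allocation.

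A reader might also infer that the arm comparison is confounded by site. Under unstratified randomisation, omitting site causes no bias in expectation and no inflation of type I error.

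Finally, the effect of .33 is for family functioning, a secondary outcome. The primary outcome is parental depression (PHQ-9), for which no effect size is given. The power figures therefore illustrate the plan's own calculation and are not power for the primary outcome.

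None of this removes the gap. Site appears in neither the allocation nor the model as described, and a site term is useful whichever way the allocation is done, unless sites hardly differ.

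**Conclusion.** The point holds as a minor improvement. Handling of site is unspecified in both randomisation and analysis. The cost is precision: at d = .33 and 144.5 completers per arm, about 0.8 or 2.0 percentage points of power at assumed site shares of 2% or 5%, compared with a stratified and adjusted design.

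It would be wrong to conclude that the sample size fails. If .33 is standardised on the total SD, between-site variance is already in its denominator, and the stated 340 reproduces without any site term.

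Clustering of outcomes by programme group within Arm 1 is a separate issue. A site term does not resolve it.

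**What to change.** 1. State whether the allocation is stratified by site.
2. Define site as one of the five delivery sites and assign every parent to one before allocation, including social-media recruits and parents who will go to the waitlist. The plan does not say how these parents get a site, and recruitment source does not coincide with delivery site, since the university is a delivery site alongside the organisations' units.
3. Randomise in concealed permuted blocks of varying size, stratified by that site. The assistant who runs the allocation needs only a site code, which is compatible with blinding to personal data.
4. Prespecify site as a fixed factor (4 df) in the primary and secondary outcome models.

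The cost is one field recorded before allocation, a setting in the randomisation program and 4 degrees of freedom. If recruitment has begun, the model term alone can still be prespecified, for about 80.1% or 81.3% power at shares of 2% or 5%, and roughly no gain at 1%.

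### Arm 1 is treated in groups at five sites, but neither the sample size nor the MANOVA allows for programme group, so standard errors are too small if outcomes correlate within groups

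*Combined protocol and SAP*

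**What the plan says.** Under Study design, the sample size paragraph reads "An estimated 340 parents will be recruited and randomised into an intervention group and a waitlist control group". It is based on an "expected effect size of .33 for family functioning" from a pilot study, 15% drop-out, a two-sided 5% level, and "80% power, and a test of two independent groups".

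Under Procedures (Implementation and assessment), "caregivers who meet inclusion criteria will be randomized into Arm 1 or Arm 2" after T0, so the unit of randomisation is the parent. The same paragraph says that "Programs are delivered in group format and will be conducted in five sites". The waitlist arm is not described as meeting in groups during the comparison.

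Under Measures, parental depression (PHQ-9) is primary and family functioning is secondary. Under Data Analyses, "All analyses will be carried out according to the intention-to-treat approach", and "MANOVA will be used to evaluate the effects of the mindful" parenting arm relative to the waitlist, for primary and secondary outcomes together.

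The protocol gives no group size, number of groups, intraclass correlation (ICC) or design effect. It names no random group effect, no cluster-robust variance and no adjustment for site.

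**The concern.** Parents in one programme group share an instructor, a site and each other's company over the sessions, so their outcomes may be more alike than those of parents in different groups. The design is then partially nested: independent parents in the waitlist arm, clustered parents in Arm 1. Both the two-sample calculation and a MANOVA without a group term treat all parents as independent.

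If the within-group correlation is positive, two things follow. The analysis reports standard errors below their true value, so confidence intervals are too narrow for every outcome, including the primary one. And the power calculation overstates what 340 parents deliver for the endpoint and test it assumes. Monitoring fidelity from recorded sessions checks that delivery is consistent; it does not account for correlated outcomes.

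**Working it through.** **Inputs from the protocol.** N = 340 randomised; d = 0.33 (family functioning), read as a standardised mean difference; two-sided α = 0.05; power 80%; drop-out 15%.

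**Assumptions (not in the protocol).** 1:1 allocation; m = 10 or 15 analysed parents per group; ICC = 0.01, 0.02 or 0.05 in Arm 1 only; total variance 1 in both arms; unadjusted comparison at one time point.

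**Step 1: reproduce 340.** n per arm = 2(1.960 + 0.842)²/0.33² = 144.15, so 288.3 in total, and 288.3/0.85 = 339.2, which rounds up to 340. Rounding to 145 per arm first gives 290/0.85 = 341.2, or 342. Either way the figure is an independent-observations calculation plus drop-out, with nothing for clustering.

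**Step 2: power under independence.** Evaluable = 340 × 0.85 = 289 (derived, not printed in the protocol), n = 144.5 per arm. SE = √(2/144.5) = 0.1176. Power = Φ(0.33/0.1176 − 1.96) = 80.1%.

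**Step 3: clustering in Arm 1.** With DE = 1 + (m − 1)·ICC:

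- Var = DE/n + 1/n; normal-approximation power = Φ(0.33/√Var − 1.96).
- Ratio of true to reported SE: R = √[1 + (m − 1)·ICC/2].
- Type I error of the test that ignores groups: 2[1 − Φ(1.96/R)]. This applies only when the average effect is zero but group effects still vary.
- Satterthwaite df = Var²/[v1²/(k − 1) + v0²/(n − 1)], with v1 = DE/n, v0 = 1/n, k = n/m groups; power from the noncentral t.

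Example, m = 10 and ICC = 0.05: DE = 1.45; Var = 2.45/144.5 = 0.01696; SE = 0.1302; power = Φ(2.534 − 1.96) = 71.7%.

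| m | ICC | DE | R | Power, normal | Power, Satterthwaite (df) | Type I error, groups ignored |
|---|---|---|---|---|---|---|
| 10 | 0 | 1.00 | 1.000 | 80.1% | 78.5% (49.2) | 5.0% |
| 10 | 0.01 | 1.09 | 1.022 | 78.3% | 76.6% (45.8) | 5.5% |
| 10 | 0.02 | 1.18 | 1.044 | 76.6% | 74.7% (43.0) | 6.0% |
| 10 | 0.05 | 1.45 | 1.107 | 71.7% | 69.4% (36.8) | 7.7% |
| 15 | 0 | 1.00 | 1.000 | 80.1% | 77.7% (32.6) | 5.0% |
| 15 | 0.01 | 1.14 | 1.034 | 77.4% | 74.6% (29.1) | 5.8% |
| 15 | 0.02 | 1.28 | 1.068 | 74.8% | 71.6% (26.4) | 6.6% |
| 15 | 0.05 | 1.70 | 1.162 | 67.5% | 63.5% (21.3) | 9.2% |

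Each power column must be compared with its own ICC = 0 row. The loss due to clustering is 80.1 − 78.3 = 1.8 to 80.1 − 67.5 = 12.6 points by normal approximation. By the Satterthwaite test it is 78.5 − 76.6 = 1.9 to 77.7 − 63.5 = 14.2 points.

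**Step 4: all 340 give data** (n = 170 per arm, normal approximation). Independence: 86.0%. For ICC 0.01/0.02/0.05: m = 10 gives 84.5%/83.0%/78.5%, and m = 15 gives 83.7%/81.3%/74.5%.

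**The case against.** Randomisation is by individual parent. If the programme affects nobody, group membership has no effect either, and the 5% level is protected. That stands: a reader might infer that false-positive risk is inflated in general, but the 5.5% to 9.2% range applies only to a zero average effect with group effects that vary around it. It does not rescue interval width when the programme works and groups differ in how well.

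Group size and ICC are assumed. That also stands. At ICC 0.01 with 10 per group the loss is under 2 points. For any positive ICC the direction is fixed; only the size is open.

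A reader might infer that the trial is underpowered for its primary outcome. The documents do not support this. The 0.33 is for family functioning, no effect size is given for PHQ-9, and the power figures describe an unadjusted comparison at one time point, whereas the plan describes a MANOVA over repeated assessments. Whether that analysis gains or loses precision cannot be told from the text. Nor is 289 a planned analysis number. The plan is intention-to-treat, and if all 340 gave data, power would stay above 80% at ICC 0.01 and 0.02 for both group sizes.

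A larger apparent loss comes from setting the Satterthwaite 77% to 64% against 80.1%. That comparison mixes tests: at ICC 0 the same Satterthwaite test already gives 78.5% or 77.7%.

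**Conclusion.** The concern holds as an omission with a definite direction and an uncertain size. The plan delivers Arm 1 in groups and makes no allowance for this in the sample size or the analysis. Under any positive within-group correlation, standard errors are understated for the primary and secondary outcomes: by a factor of 1.02 to 1.16 over the assumed range, for the simple comparison. The 80% power figure, for family functioning, has no reserve at 289 evaluable parents; over the same range it becomes about 78% to 68%. A shortfall below 80% is not certain at low ICC if fewer parents drop out than assumed.

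Clustering confined to Arm 1 further assumes that waitlist parents do not start the programme before T2. The protocol does not give that timing. The change should be made; confidence in the size of the effect is moderate at best.

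**What to change.** 1. Record each Arm 1 parent's programme group and every parent's site. Do this during delivery, because it may be hard to reconstruct later.
2. Analyse the primary and secondary outcomes with a random programme-group effect in Arm 1 only, or a cluster-robust variance with small-sample correction. Use small-sample degrees of freedom and include a site term. Without the site term, ordinary differences between the five sites, which waitlist parents may share, could be counted as programme-group variance.
3. State when waitlist parents start the programme relative to T2. Arm-1-only nesting is right only if they have not started by then.
4. Keep N = 340 and restate power with the planned group size and an ICC range such as 0.01 to 0.05, naming the endpoint and the analysed N.

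Adjusting for the T0 score is a separate, optional gain in precision. With an assumed baseline correlation of 0.5, at 289 evaluable and with Satterthwaite df, power is about 85% to 87% at ICC 0.01. At ICC 0.05 it is 79% to 81% (10 per group) or 72% to 76% (15 per group). It offsets some of the power loss but does not correct the understated standard errors.

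The cost is a slightly more complex model, about 2 to 4 points of power from the small-sample degrees of freedom (78.3 − 76.6 = 1.7 to 67.5 − 63.5 = 4.0), and a less favourable power statement.

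### MANOVA is the only between-arm method named, and the plan does not fix its responses, the PHQ-9 test, the primary visit or the handling of missing data

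*Combined protocol and SAP*

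**What the plan says.** The Data Analyses section of the combined protocol and SAP is very short. It opens with "All analyses will be carried out according to the intention-to-treat approach", supported by a citation. It then names one between-arm method: "MANOVA will be used to evaluate the effects of the mindful" parenting arm, "relative to waitlist control group (Arm 2), and the analyses of the primary and secondary outcome measures". Maintenance gets one further sentence, "In addition to the immediate programme effects, outcomes measured at T1 and T2 will be compared", with no method attached.

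Elsewhere:

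- **Measures:** "primary outcome variables include parental depression". Table 1 assigns this to the PHQ-9. Five further outcomes are secondary.
- **Implementation and assessment:** "two time points will be used to assess the intervention outcome and sustainable effect at one month and three month". Neither visit is called primary. The wording leans towards T1 (one month) for the programme effect and T2 (three months) for maintenance.
- **Study design:** both between-subject and within-subject tests are planned. The within-subject list has three labels ending in T3, whereas the schedule contains only T0, T1 and T2.
- **Sample size estimation:** 340 parents, effect size 0.33 for family functioning (a secondary outcome), 15% drop-out, two-sided 5%, 80% power, two independent groups.

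No passage gives the response vector of the MANOVA, the role of T0 in it, a separate test or estimate for PHQ-9, or a missing-data method.

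**The concern.** The primary question is whether the programme lowers parental depression. The analysis text does not identify the test that answers it.

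Two readings fit the words. The reference to primary and secondary measures together suits one joint MANOVA of six outcomes. The between- and within-subject wording under Study design suits one repeated-measures MANOVA per outcome. The documents do not settle which is meant.

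A joint test can be significant with no effect on depression at all. A repeated-measures MANOVA offers several different PHQ-9 tests with different meanings and power. Neither, as described, produces an estimated PHQ-9 difference at a stated visit. Standard MANOVA also uses only parents complete on every response entered (a property of the method, not something the documents state), which sits badly with intention-to-treat when 15% drop-out is expected.

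**Working it through.** **The plan's own figure.** Per arm, n = 2(1.96 + 0.842)²/0.33² ≈ 144.2, so 145; total 290; 290/0.85 = 341.2, so 342. An exact t-test gives 146 per arm, and 292/0.85 = 343.5, so 344. The stated 340 is reproduced within rounding. With 340 × 0.85 = 289 completers, a single two-group t-test at 0.33 has 79.8% power. The sample size itself is not in question.

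**Inputs for the rest.** From the documents: 289 completers, two-sided 5%, visits T0, T1 and T2, six outcomes. Assumed: 1:1 allocation (144 and 145); a PHQ-9 effect of 0.33 at T1 and T2 (the plan gives 0.33 only for family functioning); all correlations. Let h = 144 × 145/289 = 72.25. One-degree-of-freedom tests use a noncentral t with noncentrality d√h. Tests on p responses use Hotelling's T², a noncentral F with p and 289 − p − 1 df and noncentrality hD².

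**Joint reading.** Six outcomes at one visit, equal correlation ρ, zero PHQ-9 effect, family functioning alone shifting by 0.33: D² = 0.1089 × (1 + 4ρ)/[(1 − ρ)(1 + 5ρ)].

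| ρ | D² | Probability the omnibus test rejects |
|---|---|---|
| 0 | 0.109 | 51% |
| 0.3 | 0.137 | 63% |
| 0.5 | 0.187 | 78% |

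**Per-outcome reading.** PHQ-9 only, equal between-visit correlation r, effects 0, 0.33, 0.33 at T0, T1, T2:

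| Test | Formula | r = 0.3 | 0.5 | 0.6 | 0.7 |
|---|---|---|---|---|---|
| Arm effect averaged over T1 and T2 | d = 0.33/√[(1 + r)/2] | 93% | 90% | 88% | 86% |
| Arm effect averaged over T0 to T2, if T0 is entered | d = 0.22/√[(1 + 2r)/3] | 72% | 63% | 59% | 55% |
| Arm-by-time, 2 df | D² = 2(0.33²)/[3(1 − r)] | 68% | 83% | 91% | 97% |
| T1 and T2 jointly, 2 df | D² = 2(0.33²)/(1 + r) | 88% | 83% | 80% | 78% |
| Baseline-adjusted difference at one visit | d = 0.33/√(1 − r²) | 83% | 90% | 94% | 97% |

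If the T0–T2 correlation is r² instead of r, the arm-by-time row becomes 61/74/82/91%.

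**What the arm-by-time test means.** The changes T1 − T0 and T2 − T0 have variance 2(1 − r) and covariance (1 − r). Effects (0.33, 0.33) and (0, 0.33) give the same D², 2(0.33²)/[3(1 − r)]. So with no effect at T1 and 0.33 at T2 only, the test still rejects 68/83/91/97% of the time.

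**If the choice stayed open until the data were seen.** By simulation with no PHQ-9 effect, taking whichever of the two 2-df tests is significant gives a type I error of about 8%. Adding the average over T0 to T2 gives 10.6% to 10.8%.

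**Complete cases.** If the same 15% of parents miss all follow-up, 289 of 340 are complete. If 15% were missing independently at each of T1 and T2, 340 × 0.85² ≈ 246 would be.

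**The case against.** The strongest reply is that this is brevity, not a wrong method. The plan says outcomes are assessed at two time points after the intervention, so averaging T0 into the arm effect is an unfriendly reading. Over T1 and T2 alone the averaged test has 86% to 93% power. Per-outcome tests commonly follow a MANOVA, imputation could precede it, and recruitment already allows for 15% drop-out.

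Much of that stands, and it rules out four stronger conclusions that a reader might draw:

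- **That MANOVA leaves the trial underpowered.** In the equal-correlation table, values well below 80% occur only if T0 is averaged in, or for arm-by-time at r = 0.3. The documents do not commit to either.
- **That the plan inflates type I error.** No passage proposes choosing among tests after seeing results. The 8% to 11% measures the room left open, not a property of the design.
- **That 51 randomised parents (340 − 289) will be excluded.** This depends on the drop-out pattern and on no imputation being used. The plan is silent on both.
- **That the per-outcome reading, or the joint one, is the intended one.** The text supports either.

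The reply does not supply the missing elements. Follow-up tests and imputation are not stated. The two-group test in the sample size paragraph is a planning assumption for a secondary outcome, not a PHQ-9 analysis.

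**Conclusion.** The point holds as a gap in specification that a better primary analysis closes at little cost. That the responses, the use of T0, the PHQ-9 test, the primary visit and the missing-data method are not fixed follows from the text alone and needs no assumption.

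The sizes rest on assumed correlations and an assumed PHQ-9 effect of 0.33 at both follow-ups. On those terms, a joint test can reject in 51% to 78% of trials with no effect on depression. On the per-outcome reading, power at a given correlation differs between candidate tests by 25 points at r = 0.3 (68% to 93%) and by 42 at r = 0.7 (55% to 97%). With the T0 average left out, the gap at r = 0.7 is 19 points (78% to 97%). A significant arm-by-time test cannot be read as a programme effect at T1. Without imputation, a standard MANOVA does not deliver the stated intention-to-treat analysis; the size and direction of any bias are unknown.

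The baseline-adjusted single-visit contrast is not always the most powerful option: averaging T1 and T2 does better at r = 0.3. Its case is that it answers the primary question directly and has 83% to 97% power over the range shown.

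**What to change.** Before outcome data are analysed by arm, amend Data Analyses as follows.

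- **Primary analysis:** replace MANOVA with the baseline-adjusted between-arm difference in PHQ-9 at one named visit (T1 fits the current wording), with a 95% CI, by allocated arm, from a longitudinal mixed model using all observed visits. Since "After the first assessment (T0), caregivers who meet inclusion criteria will be randomized into Arm 1 or Arm 2", T0 is a true pre-randomisation baseline and can be used as such. ANCOVA with multiple imputation would also serve.
- **Hypothesis (ii):** use the between-arm contrast at T2 from the same model.
- **Secondary outcomes:** analyse each one separately in the same way.
- **Missing data:** state the missing-at-random assumption and add a sensitivity analysis that departs from it.
- **MANOVA:** keep it as supportive at most, with its responses and visits listed.
- **Visit labels:** correct the within-subject list under Study design to match the schedule.

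The cost is SAP wording and slightly more modelling, with no extra visits or participants. The downside is reliance on missing at random, which the sensitivity analysis probes. Because "Programs are delivered in group format", outcomes may also be correlated within programme groups. That arises whichever test is used and should be dealt with as a separate point.
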